
Name of Sponsor/Company: Kyowa Kirin Pharmaceutical Development, Inc.	Individual Study Table Referring to Part of Dossier in Which the Individual Study or Study Table is Presented: Volume: Reference:	(For National Authority Use Only)
Name of Finished Product: KHK4083		
Name of Active Ingredient: KHK4083		
(medicinal or recreational) use or active substance abuse; 22) Subject has other severe acute or chronic medical or psychiatric condition or laboratory abnormality that may increase the risk associated with study participation or investigational product administration, or may interfere with the interpretation of study results, as determined by the Investigator; 23) Subject who previously participated in a study of KHK4083. Note: A subject who was considered a Screen failure and not dosed with investigational product in the current study (4083-002) is permitted to be re-screened once due to failure to meet the Inclusion/Exclusion Criteria, whereas subjects with other reasons for lack of randomization may be re-screened twice.		
Additional Criteria to Enroll in OLE Therapy: Prior to receiving one infusion every 4 weeks of KHK4083 in the OLE, subjects must meet the following criteria: 
 1) Subjects must have completed double-blind Induction Therapy, i.e., at least five of six double-blind treatments, or the subject is already in the double-blind LTE and not beyond Week 28 with a clinical worsening or a flare of disease as defined by the Investigator); 2) Subjects must have evaluable total Mayo Clinic scores at baseline and Week 12; 3) Subjects must have been compliant with the protocol (including concomitant medication restrictions); and 4) Subjects may have no clinically significant additional risks, as determined by the Investigator or the Sponsor, of treatment with KHK4083. 		

Name of Sponsor/Company: Kyowa Kirin Pharmaceutical Development, Inc.	Individual Study Table Referring to Part of Dossier in Which the Individual Study or Study Table is Presented: Volume: Reference:	(For National Authority Use Only)
Name of Finished Product: KHK4083		
Name of Active Ingredient: KHK4083		
Number of Subjects Planned: Assuming a 15% dropout rate, it is anticipated that approximately 60 subjects will be required to be randomized in order to achieve 51 evaluable subjects in the Full Analysis Set.		
Treatment of Subjects:		
Duration of Treatment: A total of up to 52 weeks of double-blind treatment includes 12 weeks of Induction Therapy (Part A and Part B) and 40 weeks of OLE/LTE Therapy.		
Induction Therapy (12 weeks):		

 • Part A (Cohorts 1 - 3): Each subject will be administered one IV infusion of KHK4083 or placebo once every 2 weeks for a total of 6 treatments, i.e., on Day 1 (Week 0), Day 15 (Week 2), Day 29 (Week 4), Day 43 (Week 6), Day 57 (Week 8), and Day 71 (Week 10). • Part B (Cohort 4): Each subject will be administered an IV infusion of the recommended KHK4083 dose selected in Part A (one of three dose levels in Cohorts 1 - 3) or placebo once every 2 weeks for a total of 6 treatments. 		
Investigational Product:		

 • Part A (Cohorts 1 - 3): KHK4083 1.0 mg/kg (Cohort 1); 3.0 mg/kg (Cohort 2); and 10 mg/kg (Cohort 3). • Part B (Cohort 4): KHK4083 recommended dose (one of three dose levels in Cohorts 1 - 3). 		
Control (Cohorts 1 - 4): Placebo IV infusion as treatment during Induction Therapy.		
Open-label / Long-term Extension Maintenance Therapy: Week 12 (First Dose) to Week 52		
All subjects who qualify and continue double-blind LTE or start open-label maintenance therapy will be administered one KHK4083 or placebo (LTE) or one KHK4083 (OLE) IV infusion at Weeks 12, 16, 20, 24, 28, 32, 36, 40, 44, and 48 for a total of 10 additional treatments. Some subjects in the LTE may transition to the OLE after Week 12 and up to Week 28. The treatment at Week 12 will be administered at the scheduled visit or within 7 days after Week 12.		
Efficacy, Pharmacokinetics, Pharmacodynamics, Immunogenicity, and Safety Variables		
Efficacy:		
The efficacy variables include mMES, UCEIS score, modified Baron endoscopic score, total Mayo Clinic score, partial Mayo Clinic score (without sigmoidoscopy), and an IBDQ score.		
Pharmacokinetics:		
The PK variables include maximum observed serum concentration (C_{max}), time of maximum observed serum concentration (t_{max}), trough concentration at the end of the dosing interval (C_{min}), area under the serum concentration-time curve (AUC_{0-t} , $AUC_{0-\tau}$, $AUC_{0-\infty}$), terminal elimination half-life ($t_{1/2}$), systemic serum clearance (CLs), volume of distribution at steady state (V_{ss}), volume of distribution at terminal phase (V_z), and accumulation ratio (R_{ac}).		
Pharmacodynamics:		
The PD variables include the measurement of fecal calprotectin and C-reactive protein (using wr-CRP assay) concentrations. Other PD assessments include delayed-type hypersensitivity skin testing with the Candida		

Name of Sponsor/Company: Kyowa Kirin Pharmaceutical Development, Inc.	Individual Study Table Referring to Part of Dossier in Which the Individual Study or Study Table is Presented: Volume: Reference:	(For National Authority Use Only)
Name of Finished Product: KHK4083		
Name of Active Ingredient: KHK4083		

albicans antigen (at all investigative sites in the US and in other selected countries), immunohistochemical staining on all endoscopic biopsy samples, and flow cytometry analyses on whole blood or peripheral blood mononuclear cells for the measurement of specific immune-related cells.
		

Immunogenicity: For immunogenicity, the development of anti-KHK4083 antibodies will be assessed.
		

Safety: The safety variables include AEs (including SAEs), physical examinations, vital signs, body weight, 12-lead ECGs, and clinical laboratory evaluations (serum chemistry, hematology, coagulation profile, multiplex-31 assays, and urinalysis).
		

Safety Management and Monitoring: Kyowa Kirin Pharmaceutical Development, Inc. has primary responsibility for the ongoing medical review of safety data throughout the study.
 
Recommendations will be made with the input of the Medical Monitor to the Principal Investigator and other appropriate designated staff regarding further conduct of the study. The Safety Monitoring Committee will evaluate the cumulative safety data available after the first 8 subjects (1.0 mg/kg dose cohort) at Week 4. For subsequent dose escalation, the Safety Monitoring Committee will evaluate the cumulative safety data available and after the first 8 subjects in a cohort at Week 4 and with the first 4 subjects in a cohort at Week 6 for the 3.0 and 10 mg/kg dose cohorts. At each of the timepoints, the committee will assess whether dosing will continue for all subjects and if the investigational product will be administered at the next higher dose level for subjects in the next cohort in Part A or for Cohort 4 in Part B. A separate Safety Monitoring Committee Charter will identify the membership and define the specific procedures of the committee.
		

Statistical Methods and Planned Analysis: All categorical variables will be summarized by counts and percentages. Descriptive statistics (mean, standard deviation, median, minimum, and maximum) for continuous variables will be utilized. All summaries and analyses conducted will be by treatment cohort (KHK4083 dose levels; combined KHK4083; and placebo) and by visit. The last pre-administration observation will be used as the Baseline value for calculating post-administration changes from Baseline. All data obtained on the electronic case report form and entered into the database will be provided in separate data listings showing individual subject values.
 
The following analysis sets will be used in the study:
 
Safety Analysis Set: Includes all subjects who received any investigational product (even a partial dose);
 
Full Analysis Set: Includes all subjects who receive at least one full dose of investigational product and who have Baseline data and at least one post-treatment assessment of the primary efficacy variable.
 
Treatment-emergent adverse events (TEAEs) will be grouped and tabulated by the Medical Dictionary for Regulatory Activities Preferred Term and System Organ Class. All TEAEs will be summarized showing the number and percentage of subjects for each event with a start time within the Treatment Period (i.e., Induction
		

Name of Sponsor/Company: Kyowa Kirin Pharmaceutical Development, Inc.	Individual Study Table Referring to Part of Dossier in Which the Individual Study or Study Table is Presented: Volume: Reference:	(For National Authority Use Only)	
Name of Finished Product: KHK4083			
Name of Active Ingredient: KHK4083			

Therapy and LTE or OLE Therapy) and by cohort (KHK4083 versus placebo) during Induction Therapy, OLE or LTE Therapy.
 
The overall safety and tolerability of KHK4083 compared to placebo administered in multiple IV doses will be determined for all safety variables.
 
All efficacy analyses will be performed in the FAS unless otherwise specified. All statistical analyses in this Phase 2 study will be descriptive or exploratory, and no adjustment to control Type I error will be performed.
 
Pharmacokinetic, Pharmacodynamic, and Immunogenicity Methods:
 
The PK parameters (i.e., C_{max}, t_{max}, C_{min}, AUC_{0-t}, $AUC_{0-\infty}$, $t_{1/2}$, CLs, V_{ss}, V_z, and R_{ac}) for KHK4083 will be summarized by dose level and Treatment Period. The dose proportionality of KHK4083 PK exposure parameters will be assessed using the Power Model for Cohorts 1 - 3 (Induction Therapy - Part A and LTE Therapy). The PK exposure parameters include C_{max}, AUC_{0-t}, and $AUC_{0-\infty}$, as appropriate.
 
The PD parameters will be determined and summarized by dose level and Treatment Period. The PK-PD relationships will be explored using graphic tools or modeling as needed.
 
The immunogenicity of KHK4083 will be determined and the percentage of subjects with confirmed anti-KHK4083 antibodies will be summarized by dose level and Treatment Period, visit (week), and overall. The effect of positive anti-KHK4083 antibodies on the PK, and possibly efficacy and safety, will be explored.
 
Serum samples, which will be collected at specified times throughout the study, will be assessed using multiplex-31 assays at four sample collection timepoints: Baseline (Week 0), Week 2, Week 12 (End-of-Induction Therapy), and Week 52 (End-of-OLE/LTE Therapy) or at a follow-up visit if the subject does not continue in OLE/LTE Therapy. For other potential study assessments (e.g., exploratory biomarker analyses), whole blood samples will be collected and stored (frozen) for future analysis.
			

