1 SYNOPSIS

Name of Sponsor/Company: Kyowa Kirin Pharmaceutical Development, Inc.	Individual Study Table Referring to Part of Dossier in Which the Individual Study or Study Table is Presented: Volume: Reference:	(For National Authority Use Only)
Name of Finished Product: KHK4083		
Name of Active Ingredient: KHK4083		
Title of Study: A Phase 2, Multicenter, Randomized, Double-blind, Placebo-controlled Multiple Ascending Dose Study (Induction Therapy) and Long-term Extension Therapy of an Anti-OX40 Monoclonal Antibody (KHK4083) in Subjects with Moderately Active Ulcerative Colitis		
Protocol Number: 4083-002, Amendment 2		
Investigators and Study Center(s): Multicenter at approximately 40 investigative sites in the United States (US), Russia, Hungary, Poland, Romania, Serbia and Czech Republic; other countries may be included as needed.		
Phase of Development: Phase 2		

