
≤ 3 g/day) for at least 14 days prior to the Screening visit; and/or
 
 b) Glucocorticoids (≤ 20 mg/day prednisolone or the equivalent, or budesonide ≤ 9 mg/day) for at least 14 days prior to the Screening visit (or for 4 weeks if a course of corticosteroids had started at less than 8 weeks prior to Screening visit); and/or c) Azathioprine up to 3 mg/kg/day or 6-mercaptopurine up to 1.5 mg/kg/day for a total treatment period of at least 12 weeks, including 4 weeks of stable treatment, prior to the Screening visit. 
5) Subject has received any of the following prior treatments or treatments within the specified time:
 
 a) Natalizumab, efalizumab or rituximab or other lymphocyte-depleting treatments, including but not limited, to alkylating agents (such as cyclophosphamide or chlorambucil) and total lymphoid irradiation at any time prior to randomization (Baseline visit); b) TNF antagonists within 8 weeks, or 5 half-lives (based on maximum duration but not exceeding 12 weeks), prior to randomization (Baseline visit); c) Vedolizumab within 16 weeks prior to randomization (Baseline visit); d) Methotrexate, cyclosporine, mycophenolate, tacrolimus, thalidomide, or other immune altering drugs within 4 weeks prior to randomization (Baseline visit) (ophthalmologic preparations are permitted); e) 5-ASA enema, or steroid enema or suppository use within 2 weeks prior to randomization (Baseline visit); and/or f) Investigational agents within 8 weeks or 5 half-lives (if pharmacology information is available) prior to randomization (Baseline visit), whichever is longer. 
6) Subject with recent (within 1 year prior to Screening), suspected or confirmed symptomatic stenosis of the colon, abdominal abscess, or ischemic colitis based on clinical or radiographic data; or who has suspected, confirmed or a history of toxic megacolon; or with any colonic resection, subtotal or total colectomy, ileostomy, or colostomy; or who had any previous surgery for UC or an anticipated requirement for surgery for UC;
 
7) Subject with known colonic dysplasia, adenomas or polyposis;
 
8) Subject had major surgery within 4 weeks prior to Screening or an anticipated requirement for major surgery;
 
9) Subject with enteric pathogens (including Clostridium difficile) detected on stool analysis; or Clostridium difficile infection within 8 weeks prior to Screening; or intestinal pathogen infection detected within 4 weeks prior to Screening;
 
10) Subject with any of the following hematological and chemistry laboratory values:
 
 a) Platelet count < 100,000/mm³; b) Neutrophils < 1500/mm³; c) Serum creatinine ≥ 1.6 mg/dL (≥ 144.4 μmol/L); d) Alkaline phosphatase > 3 times the upper limit of normal (ULN); e) Aspartate aminotransferase or ALT > 2 times ULN; f) Total bilirubin > 2 mg/dL, unless due to Gilbert’s Syndrome; 		

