 - a) Natalizumab, efalizumab or rituximab or other lymphocyte-depleting treatments, including but not limited, to alkylating agents (such as cyclophosphamide or chlorambucil) and total lymphoid irradiation at any time prior to randomization (Baseline visit);
 - b) TNF antagonists within 8 weeks, or 5 half-lives (based on maximum duration but not exceeding 12 weeks), prior to randomization (Baseline visit);
 - c) Vedolizumab within 16 weeks prior to randomization (Baseline visit);
 - d) Methotrexate, cyclosporine, mycophenolate, tacrolimus, thalidomide, or other immune altering drugs within 4 weeks prior to randomization (Baseline visit) (ophthalmologic preparations are permitted);
 - e) 5-ASA enema, or steroid enema or suppository use within 2 weeks prior to randomization (Baseline visit); and/or
 - f) Investigational agents within 8 weeks or 5 half-lives (if pharmacology information is available) prior to randomization (Baseline visit) whichever is longer.
- 6) Subject with recent (within 1 year prior to Screening), suspected or confirmed symptomatic stenosis of the colon, abdominal abscess, or ischemic colitis based on clinical or radiographic data; or who has suspected, confirmed or a history of toxic megacolon; or with any colonic resection, subtotal or total colectomy, ileostomy, or colostomy; or who had any previous surgery for UC or an anticipated requirement for surgery for UC;
- 7) Subject with known colonic dysplasia, adenomas or polyposis;
- 8) Subject had major surgery within 4 weeks prior to Screening or an anticipated requirement for major surgery;

- 9) Subject with enteric pathogens (including *Clostridium difficile*) detected on stool analysis; or *Clostridium difficile* infection within 8 weeks prior to Screening; or intestinal pathogen infection detected within 4 weeks prior to Screening;
- 10) Subject with any of the following hematological and chemistry laboratory values:
 - a) Platelet count < 100,000/mm³;
 - b) Neutrophils < 1500/mm³;
 - c) Serum creatinine \geq 1.6 mg/dL (\geq 144.4 μ mol/L);
 - d) Alkaline phosphatase > 3 times the upper limit of normal (ULN);
 - e) AST or ALT > 2 times ULN;
 - f) Total bilirubin > 2 mg/dL, unless due to Gilbert's Syndrome;
 - g) Serum albumin < 3 g/dL;
 - h) Hemoglobin < 9 g/dL;
 - i) Glycated serum hemoglobin A1c \geq 9%.

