Hepatitis B and C, and HIV testing	hepatitis B surface antigen or hepatitis B core antibody hepatitis C antibody (If positive, do reflex to RNA by RT-PCR testing) HIV-1 antibodies, HIV-1 antigen, HIV-2 antibody		

Table 10.6.1-1 Clinical Laboratory Assessments

Tuberculosis Screening using PPD Skin Test (by investigative site) and/or IGRA (clinical laboratory) (See details in Section 7.3, Exclusion Criterion 16)
	
Standard PPD skin test or IGRA (but not both) to be performed at Screening at investigative site. If positive (i.e., PPD measures > 5 mm induration), follow up after Screening is required. An IGRA is to be performed at Screening if a subject has a history of positive PPD.
 
Note: Performing of both IGRA and PPD tests in the same subject should be avoided as Screening procedures. Positivity of one of the tests cannot be voided by negativity of the other, i.e., subjects with positive PPD and negative IGRA test performed as a part of Screening will be considered TB positive and will be required to start prophylactic anti-TB therapy prior to infusion of investigational product according to local treatment standards. All safety laboratory tests may be repeated. Screening procedures may be extended by 2 weeks.

Delayed-Type Hypersensitivity Skin Test
	
At investigative sites in the US and other identified countries, the skin tests are to be performed at Screening and Week 10. The skin testing site will be read within 48 to 72 hours following intradermal injection of the Candida albicans antigen. The largest diameter of induration will be measured in mm and collected.

Fecal Sample Analysis
	
Stool cultures to identify enteric pathogens, ova and parasite evaluations, and Clostridium difficile assays are to be performed at Screening, Week 12, and Week 52. Refer to PD assessments for fecal calprotectin measurements at Baseline (Week 0) and Weeks 2, 12, and 52.

a: A subject will be excluded from the study if a specific serum chemistry or hematology value at Screening is outside of the acceptable range as defined in Section 7.3, Exclusion Criteria.

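### Exclusion 10c prints two creatinine limits as one, but 1.6 mg/dL is about 141.4 µmol/L, not 144.4: a gap of about 3 µmol/L (2.1%)

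*Protocol*

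**What the plan says.** The Synopsis gives exclusion 10c as "Serum creatinine ≥ 1.6 mg/dL (≥ 144.4" µmol/L, with the SI figure in parentheses after the conventional one. Section 7.3 prints the same pair. Creatinine is the only laboratory limit under exclusion 10 given in two units.

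The limit is binding. Both lists require exclusion of anyone who meets a criterion, and footnote a to Table 10.6.1-1 (Section 10.6.1) applies Section 7.3 to the Screening results: "A subject will be excluded from the study if a specific serum chemistry or hematology value at Screening is outside of the acceptable range".

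The protocol gives no conversion factor, does not say which of the two figures governs, and does not state the unit in which creatinine is reported. The trial is planned at "approximately 40 investigative sites in the United States (US), Russia, Hungary, Poland, Romania, Serbia and Czech Republic".

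**The concern.** A figure in parentheses after a limit is normally read as that limit restated in another unit. If the two are not equivalent, the criterion contains two thresholds. A subject whose creatinine lies between them meets the exclusion on one figure and does not meet it on the other, and nothing in the protocol breaks the tie.

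What is at stake is the clarity of an eligibility rule, and of the record of whether it was followed. The SAP plans a listing of inclusion and exclusion violations (Listing 16.2.2-2), and Protocol Section 12.7 lets the sponsor leave a subject or value out of the evaluations because of a protocol violation. For a subject between the two limits, the protocol does not determine whether a violation occurred.

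**Working it through.** **Inputs**

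- Conventional limit: 1.6 mg/dL (Synopsis and Section 7.3).
- SI limit: 144.4 µmol/L (same places).
- Molar mass of creatinine, C4H7N3O. This is an assumption from atomic masses and is not in the documents: 4 × 12.011 + 7 × 1.008 + 3 × 14.007 + 15.999 = 113.12 g/mol.

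**Conversion factor**

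µmol/L = mg/dL × 10,000 / molar mass, so the factor is 10,000 / 113.12 = 88.40.

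**Trying to reproduce the printed SI figure**

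- 1.6 × 88.40 = 141.44 µmol/L, against 144.4 printed.
- Range over rounded factors: 1.6 × 88.0 = 140.8; 1.6 × 88.5 = 141.6.
- Factor needed to reach 144.4: 144.4 / 1.6 = 90.25, which implies a molar mass of 10,000 / 90.25 = 110.8 g/mol. No rounding of 88.40 gives this, so the printed figure is not reproduced.

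**Reverse direction**

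- 144.4 / 88.40 = 1.633 mg/dL (1.632 with factor 88.5; 1.641 with 88.0).

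**Size of the gap**

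- 144.4 − 141.44 = 2.96, about 3.0 µmol/L. With factors 88.5 and 88.0 it is 2.8 and 3.6 µmol/L.
- 144.4 / 141.44 − 1 = 2.1%.
- 1.633 − 1.600 = 0.033 mg/dL.

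**Which results are affected** (factor 88.4)

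| Creatinine, mg/dL | Same value, µmol/L | At or above 1.6 mg/dL? | At or above 144.4 µmol/L? |
|---|---|---|---|
| 1.59 | 140.6 | no | no |
| 1.60 | 141.4 | yes | no |
| 1.62 | 143.2 | yes | no |
| 1.63 | 144.1 | yes | no |
| 1.64 | 145.0 | yes | yes |

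The limits disagree from about 141.4 to below 144.4 µmol/L (1.600 to below 1.633 mg/dL) and agree everywhere else. A result of exactly 1.6 mg/dL falls inside the band: it meets the exclusion in the unit printed first but not after conversion to the second.

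**The case against.** **The conventional limit is printed to only one decimal.** 144.4 µmol/L is 1.633 mg/dL, which rounds to 1.6. At one decimal, 1.6 stands for anything from 1.55 × 88.4 = 137.0 to 1.65 × 88.4 = 145.9 µmol/L, so the gap of 0.033 mg/dL is smaller than the half-unit of 0.05. This is a fair comment on how little the gap matters, but it does not make the figures equivalent. The SI figure is printed to a tenth of a µmol/L, and a value reported as 1.6 mg/dL still meets one limit and, converted, misses the other.

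**Eligibility by country.** A reader might infer from the list of countries that a patient could be excluded at a US site and enrolled elsewhere. The documents do not support this. They do not give the reporting unit or say that it varies by site. They lean towards central testing: Table 10.6.1-1 runs the wr-CRP assay on the serum chemistry samples, and Section 10 refers to a Central Laboratory Manual for that assay. If one laboratory reports in one unit throughout, the effect is a single limit about 2% away from its printed counterpart, the same at every site.

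**Safety.** A reader might also call every subject in the band a safety error. That goes too far. Passing 10c does not make a subject eligible: exclusion 2 covers clinically significant renal history, and exclusion 22 covers laboratory abnormalities that may add risk. Each such subject is one on whom criterion 10c contradicts itself, no more.

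**Analysis.** The Full Analysis Set is defined by dosing and available assessments, and the sample size rests on feasibility. Neither uses this limit. This objection stands in full.

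**Conclusion.** The two limits printed in exclusion 10c are not equivalent. They differ by about 3 µmol/L (2.1%), and the criterion contradicts itself for creatinine from about 141.4 to below 144.4 µmol/L. The only outside input is creatinine's molar mass, and the conclusion holds for every factor from 88.0 to 88.5.

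The practical effect is small. The band is narrow, few if any subjects should fall in it, and the primary endpoint and sample size do not depend on it. It remains a correction to make, because the rule is mandatory, numeric and applied to Screening values.

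It is tempting to read 144.4 as a mistyped 141.4 and conclude that 1.6 mg/dL was meant. That is plausible but only an inference: the same pair appears in both places, and nothing in the text shows which figure came first. The choice is the sponsor's.

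**What to change.** The sponsor should state which unit governs exclusion 10c and derive the other figure from it, with enough digits that the pair agrees:

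- if the conventional unit governs, 1.6 mg/dL pairs with 141.4 µmol/L;
- if the SI unit governs, 144.4 µmol/L pairs with 1.633 mg/dL. Two decimals are not enough here: 1.63 × 88.4 = 144.1, which leaves a mismatch of 0.3 µmol/L.

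The Synopsis and Section 7.3 should carry the identical pair. It would also help to confirm which figure has been applied to Screening results, to check whether any screened subject fell in the band, and to use the same figure when compiling Listing 16.2.2-2.

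The change is one number in two places. It is not entirely free: Section 13.1 requires ethics approval of a written amendment unless a change is purely logistical or administrative or removes an immediate hazard, and altering an eligibility limit may not qualify as administrative. Including it in the next amendment would keep the added cost negligible.
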